2.9.2 HANDLING OF SUBJECTS LOST TO FOLLOW-UP WITHOUT AT LEAST ONE EVALUATION

Subjects lost to follow-up may produce bias in this study. Reasons for discontinuation will be evaluated and characterized. Subjects who do not contribute any follow-up data will not be imputed using multiple imputation.

2.9.3 HANDLING OF SUBJECTS LOST TO FOLLOW-UP WITH AT LEAST ONE EVALUATION

- If there are any patients with no follow-up (defined as not having at least one completed follow-up survey), multiple imputation (MI) (Rubin and Schenker 1991) will be used to create 20 multiply imputed data sets. This will allow patients with no follow-up to be included by imputing their follow-up outcomes in a probabilistic fashion starting with predictions based on baseline values only. The primary device group comparison using the same MMRM will be performed in at least 20 multiply imputed completed data sets with results combined using the Rubin formula, which can be implemented in SAS PROC MIANALYZE. The MI model will contain patient baseline demographic variables (age, sex, BMI, and household income) and baseline values of primary and secondary patient reported outcomes as well as values of the primary endpoint evaluated over time. It is likely that the missing data pattern will be monotonic or nearly so. If so, then monotonic regression methods will be used to obtain ‘proper’ imputations using SAS PROC MI with sporadic, low frequency missingness determined using single imputation prior to MI. If the missing value pattern is more than trivially non-monotonic, a fully conditional specification (FCS) MI approach that allows for non-monotonic missing be employed, i.e., multivariate imputation by chained equations (MICE), which can also be implemented in SAS PROC MI.

2.10 COMPARISONS AT BASELINE AND COVARIATE ANALYSIS

Baseline factors will be compared among experimental groups, including pre-dose Pain, ODI, PROMIS sleep disturbance, anxiety and depression, age, sex, race/ethnicity, education, household income, and BMI. Continuous variables will be described using means, standard deviations, median, minimum, and maximum values, and compared among groups using analysis of variance (ANOVA). Categorical variables will be described using counts and percentages and compared among groups using chi-squared or Fisher’s exact tests. Where appropriate, between group differences will be described along with 95% confidence intervals. Any baseline variables that differ among experimental groups and are associated with the outcome of interest will be included in the MMRM model to remove potential bias and improve precision.

2.11 SUBGROUP ANALYSIS

Differences in the efficacy of the investigational product will be evaluated within pre-specified subgroups of interest, defined based on key clinical factors. The primary subgroup analysis in this project will be evaluating differences based on sex (male vs. female), number of comorbidities (≤ 1 , > 1), race/ethnicity (African American, Caucasian, Hispanic, Asian), SES (above or below median), and insurance type. Analyses will include repeating the examination of the primary efficacy endpoint differences among groups within male and female, separately, as well as conducting formal statistical interaction tests evaluating evidence for effect modification in the context of the MMRM that includes all subjects. Evaluation of whether the between group differences over time are different based on strata will be based on testing the significance of the [sex]-by-[experimental group]-by-[time] interaction term in a model that includes all lower-ordered terms.

Exploratory subgroup analyses may be performed based on additional clinical characteristics (e.g., stratification based on baseline Pain [<40 vs. $\geq 40\%$]) deemed relevant by content experts to describe more fully an observed associations in primary and secondary analyses.

Heterogeneity of treatment effects will be evaluated for the named subgroups and the data presentation in the CSR will include the estimated change scores along with its 95% confidence interval (CI) within each subgroup. These results will be graphically displayed in a forest plot.

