2.4 TESTING THE PRIMARY SUPERIORITY HYPOTHESIS

Superiority testing will be performed using a mixed model for repeated measures (MMRM) analysis of covariance (ANCOVA) Model. The MMRM approach is a direct likelihood

approach requiring specialized statistical software. For this study, all MMRM parameters will be estimated using appropriate statistical software (see Software below). The MMRM model is notable for its inclusion of all available data from all eligible subjects and does not require their exclusion as in complete case analysis or arbitrary assignment of some value as in Last Observation Carried Forward (LOCF). Inclusion of outcome data from time points earlier than Week 8 informs the implicit imputation of missing Week 8 values through the covariance matrix used to model the random effects.

The random effects in an MMRM model are based on the so-called ‘unstructured covariance matrix’ in which variances over time are allowed to vary as are the pair-wise correlations over time.

The values over time include all Pain scores, namely at each and all of the 2x week follow-up time points through Week 8.

All Pain values will be included in the analysis even if they are obtained out-of-window. The fraction of out-of-window visits will be summarized at each time point.

The contrast indicated by the primary hypotheses above, $\delta(\text{pain})_{\text{EaseVRx}} - \delta(\text{pain})_{\text{sham}}$ will be estimated as the treatment group contrast from baseline to Week 8 in the Pain score derived from the MMRM. The null hypothesis is that the true value of this contrast is equal to zero. The same approach will be taken for testing both Pain Interference and Pain Intensity.

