2.4.2 DETAILS OF THE MMRM

As stated above, the covariance matrix for MMRM is an unstructured covariance matrix in which each of the variances (at every follow-up) are free to vary as are the covariances.

That is, the covariance matrix for the MMRM will not include any random effects per se, but accounts for correlations among errors by specifying the form of the covariance matrix. The MMRM employs an unstructured covariance to produce inferences that are valid under the so-called ‘missing at random’ (MAR) assumption which is more generally true than the ‘missing completely at random’ assumption that is required for validity of analyses restricted to complete cases.

The longitudinal model will be specified as a repeated measures model that expresses the Pain score as a linear function of treatment, time, treatment-by-time interaction, and a covariate of the baseline pain measurement.

The model is mathematically expressed as:

$$\mathbf{Y}_i = \mathbf{X}_i \boldsymbol{\beta} + \mathbf{e}_i$$

Where:

- \mathbf{Y}_i is change from baseline to Week 8 in Pain
- $\boldsymbol{\beta}$ is a vector of fixed-effect regression parameters which includes:
 - o μ , the overall mean
 - o θ , the treatment effect
 - o τ , a vector of post-baseline time effects
 - o η , a vector of treatment-by-time interaction effects
 - o ϕ , a vector of covariate effect parameters that only includes baseline Pain score but in general could include additional baseline variable
- \mathbf{X} is a design matrix for the fixed effects, and
- \mathbf{e} is the error vector with
 - o $E(\mathbf{e}) = \mathbf{0}$ and
 - o $Var(\mathbf{e}) = \sigma_e^2 V_{unstructured}$

The specific model to be used may be expressed as:

$$\mathbf{Y} = \mathbf{b}_{int} + \mathbf{b}_{base} + \mathbf{b}_T + \mathbf{b}_1 + \dots + \mathbf{b}_{56} + \mathbf{b}_T \mathbf{b}_1 + \dots + \mathbf{b}_T \mathbf{b}_{56}$$

With parameters as explained below.

Parameter	Represents
Y	Change from baseline
b_{int}	Model intercept
b_{base}	Baseline value
b_T	Indicator for Active Treatment
b_1, \dots, b_{56}	Indicator for each timepoint, subscripts index categorical visit with 1 being the first day of treatment, and 56 being the final day of treatment.
$b_T b_1, \dots, b_T b_{56}$	Indicators allowing varying treatment differences at each timepoint

From this model estimates of treatment effect at specific visits and specifically at Week 8 difference may be obtained as follows.

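### SAP 2.11 names only one interaction test, and that test asks whether the subgroup gap in treatment effect changes across visits, not whether it differs from zero at Week 8

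*SAP*

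**What the plan says.** The primary contrast is tied to one visit. SAP 2.4 states that it "will be estimated as the treatment group contrast from baseline to Week 8 in the Pain score derived from the MMRM". SAP 2.4.2 writes it as b_T + b_T·b_56, the treatment term plus its Day 56 interaction. The outcome in that model is change from baseline, and the time component is "a vector of post-baseline time effects", coded categorically, so baseline is not a level of time.

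For subgroups, SAP 2.11 plans:

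- separate analyses: "repeating the examination of the primary efficacy endpoint differences among groups within male and female, separately";
- interaction tests, in general terms: "conducting formal statistical interaction tests evaluating evidence for effect modification in the context of the MMRM that includes all subjects";
- one test stated exactly. Its subject is "Evaluation of whether the between group differences over time are different based on strata", and the sentence continues that this "will be based on testing the significance of the [sex]-by-[experimental group]-by-[time] interaction term in a model that includes all lower-ordered terms";
- a forest plot of "estimated change scores along with its 95% confidence interval (CI) within each subgroup".

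The named factors are sex, number of comorbidities, race/ethnicity, SES and insurance type. Nowhere does the section specify a subgroup-by-treatment contrast at Week 8.

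**The concern.** A reader of the study report will want to know whether the Week 8 benefit differs between, say, men and women. The one p-value that the SAP defines answers a different question. Because the model holds all lower-order terms, a subgroup gap that is present from the first survey and stays the same is absorbed by the subgroup-by-group term and leaves nothing for the three-way term to detect. Conversely, a difference in speed of onset that has closed by Day 56 can make the three-way term significant although the Week 8 effects are equal.

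The stake is the interpretation of subgroup results. The p-value would stand beside a forest plot about the size of the effect while testing the shape of its time course. If the general wording on interaction tests is used to add a Week 8 test, that test would be chosen later, for five named factors, without having been written down.

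**Working it through.** **Nearest stated figure.** The documents give no power for any subgroup test. The nearest figure is more than 95% power for the primary comparison with 120 + 120 (SAP 2.8.1). Simulating 20,000 bivariate-normal trials with the SAP's Table 2 means, SDs and correlations, t-tests and Hochberg-adjusted p < 0.025 gives about 96% with two-sided and 98% with one-sided p-values. The stated figure reproduces.

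**Inputs from the documents**
- SD of change to Week 8 in Intensity: 1.64 and 1.68 (Table 2). Pooled: √[(1.64² + 1.68²)/2] = 1.66.
- Evaluable: 1000 × 0.85 = 850 (SAP 2.8.1: total 1000, 15% loss).
- Visits: 2 per week × 8 weeks = 16, or 17 if Day 56 is a separate survey, as the protocol's Schedule of Activities lists it. A two-level subgroup then has 15 or 16 df for the three-way term.

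**Assumptions not in the documents.** Subgroups split 50/50; complete data; two-sided alpha 0.05; visit SDs either rising from 1.3 to 1.66 or flat at 1.66; correlation between visits a lag apart of 0.5 + 0.5 × 0.9^lag (mixed), exchangeable 0.7, or AR(1) 0.9; and the size and time course of the gap.

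**What each test tests.** Let g_v be the subgroup difference in the EaseVRx-minus-Sham effect at visit v. In the model, g_v = γ + κ_v, where γ is the subgroup-by-group term and κ_v the three-way term (zero at the reference visit).
- Three-way null: all κ_v = 0, that is, g is the same at every visit.
- Week 8 null: γ + κ_56 = 0.

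These are different hypotheses. If g is constant, every κ_v is zero whatever the value of γ.

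**Formulas.** With four cells of N/4, the estimated gap vector has covariance 16Σ/N.
- Week 8 test (1 df): SE = 4 × SD/√N = 4 × 1.66/√850 = 0.228. For a gap of 0.8, z = 3.51 and power = Φ(3.51 − 1.96) = 94%. For 0.5, z = 2.20 and power = Φ(2.195 − 1.96) = 59%.
- Three-way test: noncentrality λ = (Cg)′[C(16Σ/N)C′]⁻¹(Cg), where C contrasts each visit with the first. For constant g, Cg = 0 and λ = 0, so the rejection rate is 5% for any Σ, N or split.

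**Rejection rates (%), N = 850, 17 visits**

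| Gap over time | Rising SD: mixed / exch. 0.7 / AR 0.9 | Flat SD: mixed / exch. 0.7 / AR 0.9 | Week 8 test |
|---|---|---|---|
| Constant 0.8 | 5 / 5 / 5 | 5 / 5 / 5 | 94 |
| Constant 0.5 | 5 / 5 / 5 | 5 / 5 / 5 | 59 |
| Half-sine, peak 0.5, zero at Week 8 | 84.9 / 99.4 / 47.7 | 72.0 / 96.8 / 36.5 | 5 |
| Triangle, peak 0.5, zero at Week 8 | 72.7 / 97.8 / 37.1 | 59.1 / 92.4 / 28.6 | 5 |
| Linear rise to 0.8 at Week 8 | 71.1 / >99.9 / 37.4 | 60.2 / >99.9 / 29.2 | 94 |
| Rises to 0.8 by Week 2, then holds | 99.5 / 99.7 / 83.9 | 93.7 / 96.5 / 60.5 | 94 |

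Using 16 visits does not change the pattern.

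**Check with an estimated covariance.** In 2,000 simulated trials with N = 1000, a constant gap of 0.91 (the size of the SAP's expected Intensity effect) and an unstructured covariance estimated from the data, the three-way test rejected 5.0% and the Week 8 test 99.2%. The formula gives 5.0% and 99.1%.

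**The case against.** The best defence is that the sentence states its own scope: it concerns group differences over time, and the three-way term is a proper test of that. The preceding sentence separately plans the primary endpoint within each sex and interaction tests in the plural, so the three-way sentence may describe only the time-course question. This stands in part. The SAP does not say that the three-way term is the sole basis for judging heterogeneity, and nothing forbids a Week 8 interaction test. But none is specified, and the three-way term is the only one that is.

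A reader might infer that a lasting subgroup difference would be reported as no effect modification. The documents do not support that: the within-subgroup estimates and the forest plot would still show a Week 8 gap. They would show it without a test of the difference, since separate intervals are not such a test.

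A reader might also infer that the three-way test generally fails. It does not. The 5% figure needs the whole gap at the first survey and no change after it. The intervention is a 56-day skills programme, so a gap that builds is at least as plausible, and in some of those cases the three-way test is the stronger one.

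Finally, the subgroup tests gate no claim and carry no allocated alpha (SAP 2.12 covers only the primary endpoints and four secondary endpoints). This limits the consequence.

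**Conclusion.** The concern holds in this form: the only interaction test specified in SAP 2.11 does not address heterogeneity at the primary endpoint. That follows from the SAP's own model and needs no numerical assumption. For a constant gap its rejection rate equals alpha whatever the correlation.

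The other sizes do rest on assumptions. The 94% and 59% for the Week 8 test depend on 850 evaluable participants, equal subgroups and an SD of 1.66; unequal subgroups would lower them. The false-signal rate for a gap that has closed by Week 8 runs from about 29% to 99% according to curve, SDs and correlation, so no narrow band should be quoted. For a 0.8 gap that builds, three-way power covers about the same range, 29% to over 99%, against 94%.

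It would be wrong to read this as a defect in the primary test, the success rule or the sample size. It affects the interpretation of subgroup results and should be corrected for that reason.

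**What to change.** In SAP 2.11, name as the heterogeneity test the subgroup difference in the Day 56 EaseVRx-minus-Sham contrast, estimated from the MMRM with the three-way terms: the subgroup-by-group term plus its Day 56 three-way component. It has (number of levels − 1) df: 1 for two-level factors such as sex, 3 for the four listed race/ethnicity groups. Apply it to each named factor and report its p-value with the forest plot. Keep the full three-way test, labelled as a descriptive test of time course.

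The cost is a sentence or two in the SAP and one contrast statement per factor; no new data or model is needed. The one drawback is that the Week 8 contrast can have less power than the three-way test for some gaps that vary over time, which is the reason to report both.

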2.12 MULTIPLICITY

2.12.1 PRIMARY ENDPOINTS

A Hochberg “step-up” approach will be utilized to control overall type I error at the desired 5% level across the two primary efficacy analyses. To implement the Hochberg method, the p-values for the set of multiple null hypotheses are ordered from largest to smallest, and each p-value is compared to a sequentially decreasing alpha-level to determine whether the null hypothesis (and, potentially, subsequent hypotheses) should be rejected. Symbolically, for the set of p-values $\{p_1, \dots, p_k\}$ ordered from largest to smallest and testing the corresponding set of null hypotheses $\{H_{01}, \dots, H_{0k}\}$, the Hochberg procedure is implemented as:

Step 1: Evaluate whether $p_1 < \alpha$. If yes, reject H_{01} and all subsequent null hypotheses $\{H_{02}, \dots, H_{0k}\}$. Else, do not reject H_{01} and go to Step 2.

Step 2: Evaluate whether $p_2 < \alpha/2$. If yes, reject H_{02} and all subsequent null hypotheses $\{H_{03}, \dots, H_{0k}\}$. Else, do not reject H_{02} and go to Step 3.

[...]

Step k: Evaluate whether $p_k < \alpha/k$. If yes, reject H_{0k} . Else, none of the null hypotheses $\{H_{01}, \dots, H_{0k}\}$ are rejected and stop.

As only the smallest p-value is compared to the traditional Bonferroni-corrected α -level, the Hochberg method is more statistically powerful for controlling type I error in the context of testing multiple null hypotheses. Hochberg also shows that this method is generally more statistically powerful than the Holms step-down procedure. This method of multiplicity was selected given the expectation that the endpoints are not negatively correlated. Should the observed data be negatively correlated, a bootstrapping approach for multiplicity will be provided in addition to the Hochberg correct. Therefore, the Hochberg step-up procedure achieves the goal of maintaining overall type I error at the desired α -level across a set of null hypotheses, while also improving statistical power over other approaches. The adjusted p-values from this procedure will be considered the primary study results.

2.12.2 SECONDARY ENDPOINTS

The following secondary endpoints will be adjusted for multiplicity using the same methodology as the primary endpoint:

- ODI
- PROMIS sleep disturbance
- PROMIS anxiety
- PROMIS depression

3 OTHER ELEMENTS OF THE ANALYSIS PLAN

3.1 SUBJECT DISPOSITION

Subject disposition will be reported in accordance with the 2004 FDA Guidance for Clinical Data Presentations for Orthopedic Device Applications (see References).

A subject Accounting Table will include at least the following elements:

Theoretical follow-up: The theoretical follow-up is the number of subjects that would have been examined if all subjects were evaluated on the exact anniversary of their respective initial treatment dates.

Cumulative deaths: Cumulative deaths up to the date of the exact anniversary defining the current interval. Deaths occurring after the exact anniversary are recorded in the next interval.

Not Yet Overdue: Includes subjects whose anniversary has occurred; however, clinical data has not yet been collected (e.g., BPI is unavailable) but the subject is still in the protocol specified follow-up window. Such subjects may yet be observed and so follow-up compliance estimates account for this by removing such subjects from the denominator as well as from the numerator when determining compliance ratios.

Expected due for clinic evaluation: This row is the number of subjects expected for a given time interval. These include the theoretical number of subjects who were due to be evaluated, less the number of subjects who died by that time interval and less the subjects in the “Not yet overdue” category.

Visit Compliance (%): These rows indicate the percentage of subjects compliant with the specified visit scheduled for all evaluated subjects among expected due subjects, and separately, for all subjects that are within the window among expected due subjects.

3.2 SAFETY ANALYSIS

Assessment of the safety of the investigational device will include an evaluation of the incidence and severity of complications and adverse reactions associated with the treatment. Primary safety comparisons will be performed using the mITT analysis set.

Adverse event rates will be summarized by type of AE and for specific AEs in two ways:

1. Per subject incidence of specific AEs and classes of AEs
2. By event, summarizing event counts by visit interval over time and in accordance with FDA Guidance (CDRH 2004).

Events will be summarized by severity and relatedness.

The summary tables will show the adverse events (in coded terms), the total number of events, and the number and the percentage of subjects affected in the investigational group

(“subject wise evaluation”) and stratified by relation to device and severity. Data of dropouts will not be presented separately, but possible bias will be discussed in the final report.

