- **Dynamic breathing modules:** based on evidence-based biofeedback training designed to enhance awareness of one's physiological response to pain and to self-regulate that response. In a virtual world, the user experiences a gamified biofeedback session where they are introduced to awareness of their breath via visualization in the virtual environment in the form of air bubbles. In multiple sessions, the user receives increasingly challenging tasks to practice diaphragmatic breathing while interacting with the virtual environment. The user is also asked to pace their breath according to an expanding and contracting ring in the environment to slow their breath and create physiological changes associated with relaxation. The user's exhale is measured by the microphone embedded in the Pico G2 hardware, offering biodata-enabled immersive therapeutics.

Sham VR

In an ongoing systematic literature review using Cochrane criteria, few VR studies have been found that adequately blind participants to the treatment procedure. VR-CORE guidelines suggest using an active control in VR clinical trials and promote the use of non-immersive, 2D content within a VR headset as an optimal control. Thus, participants in the Sham VR group will receive the same Pico G2 4K headset as participants in the immersive VR groups, but rather than view 360-degree, 3D, interactive content specially selected for efficacy, they will only have access to 2D nature footage with neutral music layered on top that is selected to be neither overly relaxing nor distracting. The experience of Sham VR is similar to watching a large-screen TV, but it is not interactive. The advantage of Sham VR is that it controls for the novelty and immersion of the hardware and isolates the effect of VR skill-based training.

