16 SAFETY REPORTING

Participants will be carefully monitored during the study for possible adverse events (AEs) from the time they start treatment or sham to the time of study completion. All medical events and conditions prior to

this time point are to be captured as medical history. Any observed AE will be fully investigated by the Investigator and classified in line with the definitions below.

All adverse events that occur during this study will be recorded on the adverse event eCRFs and must include the following information at minimum:

- Event Description
- Date of Onset
- Date of Resolution
- Severity
- Seriousness
- Relationship to Study Device/Procedure
- Outcome

Adverse events will be recorded and classified by the research team, including a medical doctor on staff, using the specific signs, symptoms, or medical diagnosis if no signs or symptoms can be identified.

Significant new information and updates should continue to be captured in the participant's records and in the EDC as they become available and the adverse event should be followed until it is resolved or no further improvement is expected, or the participant is lost to follow-up. The Investigator will record all AEs regardless of whether they are anticipated or unanticipated and regardless of classification, seriousness, intensity, outcome, or causality.

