1.8.2 MODIFIED INTENT TO TREAT ANALYSIS SET (mITT)

For the primary analysis and safety evaluations, the mITT Analysis Set will be defined and presented as primary. The mITT Analysis Set includes all enrolled subjects who actually receive the device. If all enrolled subjects receive the device, the mITT and ITT Analysis Sets will coincide and will be referred to as the ITT Analysis Set.

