2 EFFICACY EFFECT ANALYSES

2.1 DESCRIPTIVE ANALYSIS

Observed values within the four (4) experimental groups and differences among groups in primary and secondary endpoints will be summarized using descriptive statistics, including means, standard deviations, medians, minimum, and maximum values for continuous data, and frequencies and percentages for categorical data. 95% Confidence or Credible Intervals will be provided for all analysis and provided with clinical interpretations in the Clinical Study Report. Graphical analyses of most variables will be provided with summary statistics including standard error or posterior interval markings.

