3.3 PROTOCOL DEVIATIONS

Protocol deviations will be summarized by experimental group.

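### SAP 3.2 plans safety comparisons, but its adverse-event table sentence names only the investigational group and specifies no sham column

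*SAP*

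**What the plan says.** SAP 3.2 (Safety Analysis) contains three statements that bear on the point.

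- Comparison: "Primary safety comparisons will be performed using the mITT analysis set". The groups, the measure and the estimate to be compared are not stated.
- General summary: "Adverse event rates will be summarized by type of AE and for specific AEs in two ways", namely incidence per subject and event counts by visit interval. This is neither restricted to one arm nor specified by arm.
- Table content: the tables list coded events, total event counts, and "the number and the percentage of subjects affected in the investigational group", broken down by relatedness and severity. Sham is not mentioned.

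SAP 1.8.2 defines the analysis set: "The mITT Analysis Set includes all enrolled subjects who actually receive the device". Elsewhere the SAP does name groups. SAP 3.3 states "Protocol deviations will be summarized by experimental group", and SAP 2.1 covers all four groups, but for primary and secondary endpoints.

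Protocol 16 monitors participants for "possible adverse events (AEs) from the time they start treatment or sham to the time of study completion". Protocol 7.4 says "participants in the Sham VR group will receive the same Pico G2 4K headset as participants in the immersive VR groups".

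**The concern.** A safety comparison needs an incidence in each group. The one sentence that tells a programmer what the adverse-event tables contain gives subject counts and percentages for one side.

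The missing side matters here because of what the control is for. Protocol 7.4 presents Sham VR as the control for the novelty and immersion of the hardware. A headache or dizziness in an EaseVRx participant may come from the content, from wearing a headset, or from ordinary background illness, and only the sham incidence separates the first from the other two. Protocol 16.4 collects events through the last follow-up whether or not they are thought related to the device, so over 24 months many will be background. Breaking the table down by relatedness does not replace a control: under Protocol 16.3 relatedness is a clinical judgement that must itself allow for concomitant treatment and natural history.

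**Working it through.** The plan states no figure on this point, so there is none to reproduce. The check is a comparison of the texts, followed by an illustration of what a one-group table can and cannot show.

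**Step 1. Does the mITT set contain sham participants?** SAP 1.8.2 makes mITT the set for the primary analysis and for safety, and includes everyone enrolled who receives a device. SAP 2.2 makes the primary analysis a comparison of pooled EaseVRx with pooled Sham. The set must therefore hold both groups, and a safety comparison within it is naturally EaseVRx against Sham.

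**Step 2. Does any other sentence supply the sham column?**

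| Place | Subject | Group wording |
|---|---|---|
| SAP 3.2, comparison sentence | Safety | Analysis set only; groups and measure not stated |
| SAP 3.2, general rates sentence | Adverse events | None |
| SAP 3.2, table sentence | Adverse events | Investigational group |
| SAP 3.3 | Protocol deviations | By experimental group |
| SAP 2.1 | Primary and secondary endpoints | Four groups and differences; adverse events not named |

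None does so expressly. The comparison sentence implies a sham rate, and the table sentence leaves it out.

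**Step 3. What does a one-group figure leave open?** Inputs: about 1000 participants randomized 1:1:1:1 (Protocol 9.1), so 1000 × 2/4 = 500 per pooled group, ignoring any who never receive a device. All incidences below are assumptions, because the documents give no sham rate. EaseVRx is set at 10%, and Sham is varied over 10%, 5% and 2%.

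For one group the 95% CI is p ± 1.96 × √[p(1 − p)/n]. With p = 0.10 and n = 500, the standard error is √(0.09/500) = 0.01342, giving 7.37% to 12.63%.

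For the difference it is (p_E − p_S) ± 1.96 × √[p_E(1 − p_E)/n + p_S(1 − p_S)/n]:

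| EaseVRx | Sham (assumed) | Standard error | Difference, points (95% CI) |
|---|---|---|---|
| 10% | 10% | √(0.000180 + 0.000180) = 0.01897 | 0.0 (-3.72 to 3.72) |
| 10% | 5% | √(0.000180 + 0.000095) = 0.01658 | 5.0 (1.75 to 8.25) |
| 10% | 2% | √(0.000180 + 0.0000392) = 0.01481 | 8.0 (5.10 to 10.90) |

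The EaseVRx entry is the same in all three rows. Taken alone, it cannot tell no excess from a clear one.

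**The case against.** The strongest reply is that this is loose drafting and that no one intends to leave sham out. The table sentence does not contain the word *only*. The rates sentence and the instruction to summarize by severity and relatedness carry no arm limit, and a comparison in the mITT set cannot be run without sham rates. The group qualifier may attach only to the last item in its list, the number and percentage of subjects. The by-event summaries are to follow an FDA guidance whose layout cannot be checked from these documents and might call for control columns.

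Much of this stands, and it rules out stronger readings. A reader might infer that about 500 sham participants drop out of the safety reporting. The documents do not support that: Protocol 16 collects adverse events in sham participants, so tables by arm can be produced at any time, and the other sentences in SAP 3.2 do not exclude them. A reader might also infer that cybersickness would have no sham rate. That does not follow either. The Schedule of Activities (Protocol 6.2) gives the VR Sickness Questionnaire weekly during treatment with no arm restriction, and Protocol 14.1 places it under secondary outcomes, so SAP 2.1 may already cover it by group. That cover is not certain, since neither the secondary aims in Protocol 8 nor SAP 2.5 lists the questionnaire.

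What the reply does not remove is the conflict itself. The number and percentage of subjects affected is the quantity a comparison of incidence needs, and it is the item tied to one group. SAP 3.3 shows that by-group reporting was written out where it was specified.

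**Conclusion.** The point holds as an internal inconsistency in SAP 3.2: a comparison is promised, and the table rule omits the comparator. Taken literally, that rule would give adverse-event tables without the same-headset control needed to attribute an excess to the EaseVRx content.

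The consequence is limited. It concerns the specification of tables and leaves data collection, the primary efficacy analysis, the sample size and the type I error untouched. The illustrative differences of 0 to 8 points rest on assumed incidences and on 500 per pooled group; they show what a one-group figure leaves undetermined and are not predictions for this trial. The correction should be made before the safety tables are programmed, so that the comparison is defined in advance.

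**What to change.** In the table sentence of SAP 3.2, replace the restriction to the investigational group with: *in each experimental group (pooled EaseVRx and pooled Sham through Day 56; by the four arms thereafter)*. The split follows SAP 2.2, which pools because the arms differ only after week 8.

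Add one sentence defining the comparison: the difference between pooled EaseVRx and pooled Sham in the proportion of subjects affected, with a 95% CI, in the mITT set. It would help to state in the same edit how the VR Sickness Questionnaire is summarized by arm, since SAP 2.5 does not list it.

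The cost is a phrase, a sentence and extra table columns. The data are already collected, and no study procedure changes.
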